## 5. Introduction

### 5.1. Background

An estimated 8.5 million people in the United States will have heart failure (HF) by 2030 [1], and approximately 50% of these HF patients will have a preserved ejection fraction (HFpEF) [2]. In contrast to HF with reduced EF (HFrEF), no effective drug or device therapies have been identified that improve the prognosis of the disease.

A large proportion of HFpEF patients have hypertension and have a concentric hypertrophic (CH) etiology described as an increased heart mass with increased relative wall thickness [3]. Cardiomyocytes in HFpEF are thicker than HFrEF, and collagen content is increased compared to controls [4]. Patients with concentric hypertrophy or evidence of increased wall thickness are characterized by an increase in end diastolic pressures and isovolumic relaxation time [5] compared to normal controls. HFpEF patients have relatively normal volumes and EF, but they have a reduced ability to adequately fill a stiffened left ventricle (LV). The impact of this diastolic dysfunction is more notable during exercise; HFpEF left ventricles are reliant on high left atrial pressures to fill the LV [4]. A search for a therapy that improves the compliance of the ventricle and improves early diastolic filling in these patients has not been successful.

We are proposing a pacing therapy that titrates a bolus of atrial pacing at 100 bpm delivered during sleeping hours with the hypothesis that raising heart rates can promote a beneficial LV dilation, which will reduce chamber stiffness and improve diastolic filling in HFpEF patients that have thickened ventricular walls and normal to small LV volumes. One challenge is finding a therapeutic heart rate dose that does not cause undesirable symptoms in ambulatory HF patients and a dose that achieves a desirable level of dilation to improve filling. Studies in animal models show that the dilatory effects of rapid pacing diminishes once the elevated pacing rates are discontinued [6-8] ; the study of dose response to elevated atrial pacing rate also includes monitoring the reaction of the heart to withdrawal of the pacing therapy.

Clinical studies of SupraVentricular Tachycardia (SVT) rates and durations that cause LV dilation are limited. An extreme example of elevated heart rates promoting significant dilation and LV dysfunction comes from the clinical observation of SVT induced cardiomyopathy. Medi et al [9] reported 10% incidence of tachycardia induced dilated cardiomyopathy (TIC) in N=345 patients undergoing ablation for atrial tachycardia. EF improved from  $35 \pm 11\%$  to  $59 \pm 3\%$  in the 2 months post-ablation. At the time of ablation treatment, the patients with LV dilation were characterized by slower ventricular response rates ( $117 \pm 21$  bpm vs  $132 \pm 33$  bpm,  $p=0.05$ ) and these patients reported that the duration of their symptoms started one or more years before seeking treatment. Conventional wisdom is that patients with more rapid ventricular responses are symptomatic and seek treatment more quickly before dilation and cardiomyopathy can occur from the rapid SVT.

Animal studies that have been used to study TIC have reported LV dilation and increased pulmonary capillary wedge pressures within 1 to 3 weeks when hearts are paced at extremely fast rates such as 240bpm [6]. However, the extent of dilation and symptoms can be titrated by choice of pacing rate and the duration of pacing. A study in a porcine model of concentric hypertrophy showed that 100% atrial pacing at 170bpm increased LV end-diastolic volumes by 246% in 4 weeks of pacing compared to an increase of 25% at a more modest rate of 125 bpm at 2 weeks of pacing (about 30bpm higher than normal sinus rhythm). The atrial pacing rate of 125bpm did not cause measurable changes in biomarkers including B-type natriuretic peptide [7].

Since this therapy is delivered in an ambulatory patient, the choice of pacing rate and duration to achieve a therapeutic dilation of the LV must not induce intolerable symptoms. A rate of 100bpm may be suitable for most HFpEF patients to respond favorably to stimulus rate, without symptoms. The nominal pacing rate setting for "Activities of Daily Living" (ADL) in Medtronic pacemakers is 95bpm and the upper pacing rate (UR) is 130 bpm, so a sustained pacing rate of 100bpm is well within normal pacing range [10]. The acute hemodynamic response to elevated pacing rates in supine patients with CH has been characterized to have a blunted inotropic response to pacing rates above 100bpm compared to normal subjects [5]. Stroke volumes have been shown to decrease from baseline as atrial pacing increases the rate above 120bpm in supine patients [5, 11, 12]. The force-frequency effect was reported to be positive at rates 20 and 40bpm above intrinsic rates in patients with left ventricular hypertrophy (LVH) [11]. However, Inagaki et al [13] showed that the force frequency relationship can be biphasic in some patients with severe LVH, with a decrease in LV max +dp/dt observed in some patients as pacing rates increased above a range of 100-130bpm. At a structural level, HFpEF is typically associated with concentric remodeling with an increased left ventricular (LV) mass-to-volume ratio or overt LV hypertrophy and fibrosis. A high prevalence of this structural phenotype in HFpEF was recently confirmed in the Treatment of Preserved Cardiac Function Heart Failure with an Aldosterone Antagonist (TOPCAT) trial [22]. Despite the inclusion of patients with LV chamber dilation in this trial, about a quarter of patients had below-normal chamber volumes.

Pacing at an elevated rate for 100% of the day may accelerate changes in cardiac structure, but could be symptomatic if elevated rates sustained for long periods of time. Elevating heart rate for 5 hours during sleep at night may reduce the sensation to elevated rates and minimize symptoms for the patients. However, a heart rate dose of 5 hours will increase the overall duration required to promote dilation in the LV chamber. A measurable change in LV volumes was measured at 2 weeks of 100% pacing at 125bpm in animals [7], so a reasonable therapy duration of 100bpm for 5 hours per day would be 4 to 8 weeks of pacing before changes in LV volume would be measured. Measurement of biomarkers including matrix metalloproteinases (MMPs) and tissue inhibitors of metalloproteinases (TIMPs) may be useful in understanding the time course of changes that lead changes in geometry. The matrix metalloproteinases (MMPs) are part of an enzymatic system that contribute to the remodeling of the extracellular matrix during rapid pacing-induced cardiomyopathy [14]. MMP-1, MMP-2, and MMP-3 were shown to increase in abundance at 7 days following initiation of rapid pacing, and were temporally related to a measured decrease in the collagen content as well as a lengthening of cardiomyocytes. TIMPs are also involved in inhibiting MMPs enzymatic activity and elevated TIMP-1 with reduction in MMPs were reported in HFpEF patients with LV hypertrophy [15].

This proposed elevated atrial rate pacing therapy is aimed at improving exercise capacity in HFpEF patients. In order to safeguard patients, we propose measuring blood biomarkers including troponin and NT-proBNP in order to monitor indications that the therapy is not causing ischemia or worsening heart failure. Natriuretic peptide release occurs in response to myocardial stretch. BNP and NT-proBNP are moderately elevated in HFpEF patients and may drop to normal levels in symptom-free periods [16]. The European Society of Cardiology guidelines propose a cut-off of >35 pg/ml for BNP and >125 pg/ml for NT-proBNP to identify chronic, stable HFpEF patients [17]. Thresholds for acute HF have been reported as 100pg/ml for BNP and 300 pg/ml for NT-proBNP, which give sensitivity of 0.95 and 0.99 respectively, and negative predictive value of 0.94 and 0.98, respectively [18]. In a study of patients hospitalized for acute decompensated heart failure, a positive Troponin test for myocardial infarction was defined using a threshold of 1.0 µg/L or higher for cardiac Troponin I or 0.1 µg/L for cardiac Troponin T [19]. In an ambulatory chronic HFpEF population in 157 patients, the median value for Troponin I was 14 pg/mL (0.014 µg/L) [20]. A Troponin T threshold of 0.02 ng/mL (0.02 µg/L) was used in ambulatory HFpEF patients to detect myocardial injury; patients that had elevated Troponin T had an 78% rate of death or hospitalization at 18 months compared to 13% [21].

Metrics that will be used to evaluate whether there is a measurable therapeutic effect of the elevated atrial pacing rate therapy include serial measurements of quality of life, 6 Minute Walk Test, device-measured activity, echo measurements of volumes and diastolic function, and chronic changes in resting heart rate.

## 5.2. Purpose

Medtronic, Inc. is sponsoring the REVAMP study, a multi-center, prospective, randomized, single-blinded, clinical feasibility study. The REVAMP clinical study will include market-released pacemaker devices that incorporate the Sleep function. The purpose of the REVAMP Clinical Study is to assess whether elevating the atrial pacing rate for temporary periods of time is feasible. Data will be collected to characterize whether temporary atrial pacing rate elevation can lead to beneficial left ventricular (LV) chamber dilation, improvements in exercise capacity, and quality of life in a specific etiology of Heart Failure with Preserved Ejection Fraction (HFpEF) patients who have normal to small LV chambers and evidence of thickened walls.

## **6. Objectives and Endpoints**

### **6.1 Objectives**

#### **6.1.1. Primary Objectives**

The primary objective of this study is to assess the feasibility of using elevated night pacing as a therapy for HFpEF patients.

#### **6.1.2. Ancillary/Exploratory Objectives**

Adverse events, Minnesota Living With Heart Failure (MNLWHF) Questionnaire responses, EQ-5D-5L Questionnaire responses, 6 Minute Walk Test distances, resting heart rate, atrial fibrillation incidence, device-measured activity levels, echo measurements and blood samples will be collected at Baseline and follow-up visits as detailed in Section 10. Study Procedures. Adverse events will be collected as described in Section 12.1. Adverse Events and will be characterized to assess the overall safety and tolerability of the therapy, as described in Section 12.5.1. Adverse Event and Device Deficiency Classification. Changes in NT-proBNP and troponin concentrations from Baseline will also be used to assess patient safety. Early study patient withdrawals over the course of the study will be used to further assess therapy tolerability. Changes in quality of life, as assessed by the MN Living With Heart Failure and EQ-5D-5L, changes in 6 Minute Walk Test distance and change in activity levels will be compared from baseline to the various follow up time points to assess for therapy efficacy. Echo measurements and, optionally, peripheral blood concentrations of extracellular matrix biomarkers will be characterized and changes will be correlated with changes in the safety and efficacy assessments. End diastolic volume and mitral deceleration time could increase if the therapy works as hypothesized. If the quality of life, changes in 6 Minute Walk Test distance and/or activity levels improve, it will be of interest to see if the end diastolic volume and mitral deceleration time correlate with improvements. If the therapy works as hypothesized, other echo measurements, including left ventricular ejection fraction (LVEF), might also change over time, although the direction and magnitude of these effects are difficult to predict. Characterizing these effects will be an important goal of the feasibility study.

### **6.2. Endpoints**

As part of the exploratory/ancillary safety, tolerability and efficacy effects described in Section 14.1. Endpoint Definitions, it will be of interest to characterize changes in collected measurements from Baseline to 4 weeks, compare changes in collected measurements at 4 weeks to 8 weeks in the subjects randomized to the elevated night pacing ON arm to subjects randomized to the elevated night pacing OFF arm and compare changes in collected measurements at 12 weeks to Baseline, 4 and 8 weeks to see whether any therapeutic improvements are sustained after the therapy is discontinued.

#### **6.2.1. Primary Endpoint**

As a feasibility study, this study is not powered to meet any specific endpoints.

## 7. Study Design

The REVAMP Clinical Study will be a multi-center, prospective, randomized, single-blinded, clinical feasibility study. Subjects will be randomized in a 2:1 ratio to elevated night pacing ON or elevated night pacing OFF.

[figure not shown]
It is expected that up to 50 subjects may be enrolled to ensure approximately 30 subjects undergo elevated night pacing at approximately 10 sites in the United States to ensure enrollment completion within the pre-specified timeframe.

The REVAMP study will be conducted as a Non-Significant Risk (NSR) IDE study. The REVAMP Research System does not include an investigational device; the ability to program a lower rate of 100 bpm is available in market-released pacemakers, and the Sleep function (which allows a different rate to be programmed for part of a 24 hour clock) is an approved feature in market-released pacemakers that will be used in the clinical study. The study will be conducted in compliance with 21 CFR Parts 11, 50, 56, 812.2(b)(1). This study does not require an IDE submission to FDA.

The Sleep Function will be programmed so that the pacemaker can deliver an elevated pacing rate of 100 bpm during the night for 5 hours and lower the rate during the daytime hours. This is within the FDA-approved programmable parameters of the Sleep Function feature. The associated minimal risk will be minimized as described in Section 11.2. Risk Minimization.

The study will collect the following information: demographics, medical history, medications, standard physical, NYHA class, blood samples to measure NT-proBNP, Troponin and other biomarkers, echo measurements, MN Living with Heart Failure Questionnaire, EQ-5D-5L Questionnaire, 6 Minute Walk Test, implanted device information, device interrogations, save-to-media, adverse events (including death), system modifications, and exit information. The MN Living with Heart Failure Questionnaire was chosen to measure the quality of life for subjects with heart failure, which includes a question on how well the subject is sleeping at night.

See Section 10. Study Procedures. for further detail on study procedures and data collection as well as time-points for data collection.

**Figure 1: In Office Study Visits**

### 7.1. Duration

The study duration is expected to be approximately 24 months. This represents 21 months for subject enrollment and 3 months for subject follow-up after the last subject is randomized. Subjects are anticipated to be in the study for approximately 12 weeks completing in office visits at Enrollment/Baseline, 4 weeks, 8 weeks, and 12 weeks. Subject's device programming will be returned to standard pacemaker device settings per physician discretion at either 4 or 8 weeks after initiation of elevated night pacing, and subjects will be exited after completing the 12 week visit.

### 7.2. Rationale

It is expected that up to 50 subjects may be enrolled to ensure approximately 30 subjects will have elevated night pacing programmed ON for the first 4 weeks in order to evaluate whether the therapy is symptomatic. Limitations to the programming of the Sleep Function requires subjects to have a lower

rate of 100bpm programmed between the time they leave the Baseline visit and 5am the next morning when "Bed Time" will set the Sleep Rate at the pre-study lower rate of 60-70bpm. At the 4 week visit, there will be a safety assessment. Measurements of NT-proBNP will be used to assess whether dilation of the heart is signalling worsening heart failure. A Troponin assay will be used to ensure the elevated night pacing therapy isn't leading to ischemia. Subjects will be randomized at 4 weeks to elevated night pacing ON or OFF in order to gather data on the dose-response of the elevated night pacing therapy. Some patients may have sensation of an elevated heart rate from this programming, making blinded randomization difficult to achieve. All subjects will be followed for at least 4 weeks following termination of the elevated night pacing therapy in order to evaluate whether changes in quality of life, 6 minute walk tests and echo measurements persist after the therapy is discontinued. Previous work in animal studies have shown that cessation of elevated pacing rates can reverse the dilation of the LV chamber; this study will monitor the time course of that reversal by serial echo measurements, 6 minute walk tests and activity counts, and quality of life assessments.

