**Table 4: Study Procedures**

Study Procedure	Enrollment	Baseline	Telephone Call Follow Up Visits (24 Hour, 5 days, 2 weeks, 6 weeks, 10 weeks)	4 week visit	8 week visit	12 week visit (Study Exit)	Early Study Exit	Unscheduled Visit
Informed consent	x							
Inclusion/exclusion	x	x						
Demographics		x						
Medical History		x						
Medications		x	X	x	X	x	X	x**
Physical Assessment		x		x	X	x		x**
NYHA class		x		x	X	x		
MN Living with Heart Failure Questionnaire		x		x	X	x		
EQ-5D-5L Questionnaire		x			X			
6 Minute Walk Test		x		x	X	x		
Echo		x		x	X	x		x**
Blood Draw		x		x	X	x		x**
Initial Device Interrogation/Save-to-media		x		x	X	x	x	x**
Device Programming		x		x*	x*		x**	x**
Final Device Interrogation/Save-to-Media		x		x	X	x	x	x**
At least 30 minute observation period post device programming		x						
Symptom Assessment			X	x	X	x		x**

Study Procedure	Enrollment	Baseline	Telephone Call Follow Up Visits (24 Hour, 5 days, 2 weeks, 6 weeks, 10 weeks)	4 week visit	8 week visit	12 week visit (Study Exit)	Early Study Exit	Unscheduled Visit
Heart Rate (using finger oximeter)			X					
Crossover			As they occur					
System modifications	As they occur							
Adverse events (AEs)/Death	As they occur							
Device Deficiencies	As they occur							
Study deviations	As they occur							
Study Exits	As they occur							

\* See programming recommendations for the follow up visit

\*\* If deemed necessary by the investigator

Table 5 below specifies permitted time windows for the required subject visits. Should a subject miss a visit or the visit falls outside the pre-specified window, a study deviation must be reported and the original follow-up schedule maintained for subsequent visits. Data analyses will include follow-up visits, regardless of whether the visit occurs within the window. Therefore, a late visit is preferred over a missed visit but must be accompanied by a deviation.

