### 10.11. Randomization (4 Week Follow-Up)

Subjects will be assigned to a group at random during the randomization visit. Randomization will occur at 4 weeks.

Subjects will be randomized in a 2:1 ratio to the Elevated Night Pacing ON or to the Elevated Night Pacing OFF group.

Sites will receive this randomization assignment from the randomization schedule, which is automatically populated on the eCRF.

Procedures to be performed and data to be collected at Randomization include:

- Physical Assessment (including weight, heart rate, symptoms, and blood pressure)
- Medications
- NYHA Class
- MN Living with Heart Failure Questionnaire
- 6 Minute Walk Test
- Echo\*
- Blood Draw\*\*
- Randomization assignment
- Device Interrogation/ (initial)
- Save-to-Media (initial)
- Device Programming, see Table 7: Programming Recommendations at 4 Week Follow-Up
- Device Interrogation (final) - this needs to be completed at the end of the visit after programming has been completed
- Save-to-Media (final)
- Adverse Events (report new/assess ongoing AEs), Study Deviations, System Modifications, Device Deficiencies, Crossovers (as they occur)

\*The echo must be sent to the Echo Core Laboratory for analysis, with a copy of the echo remaining at the site. Details of the Echo Core Laboratory, type of echo to be performed, and the review process will be provided in an Echocardiography Handbook (provided under separate cover).

\*\* The blood sample must be sent to the Blood Core Laboratory for analysis. Details of the blood core lab and the blood draw process will be provided under separate cover.

For any subject who has an abnormal NT-proBNP, troponin or LVEF measurement as defined in the Safety Assessment (Section 10.19. Assessment of Safety) and the investigator elects to discontinue elevated night pacing, a subsequent visit will be necessary for the elevated night pacing to be programmed OFF if the subject was randomized to the elevated pacing ON arm. The subject should continue to be followed through the 12 week visit.

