### 10.12.1. Programming Recommendations

Table 8 lists the programming recommendations applicable to study subjects who still have elevated night pacing ON. (All subjects should have elevated night pacing OFF by the end of the 8 week visit.)

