### 10.14. **12 Week Visit (Study Exit)**

At the completion of the 12 week follow-up visit, subjects will be exited from the study since this is the final visit. The 12 week follow-up visit and exit visit should be combined, and both a 12 week follow-up eCRF and a Study Exit eCRF need to be completed. The following procedures must be performed / data are required to be collected at the 12 week visit:

- Medications
- Physical Assessment (including weight, heart rate, symptoms and blood pressure)
- NYHA Class
- MN Living with Heart Failure Questionnaire
- 6 Minute Walk Test
- Echo\*
- Blood Draw\*\*
- Device Interrogation (initial)
- Save to Media (initial)
- Program the sleep function and pacing parameters to elevated night pacing OFF (see Table 8) for subjects who still have their pacemaker programmed to elevated night pacing ON.

- Device Interrogation (final) - this needs to be completed at the end of the visit after programming has been completed
- Save-to-Media (final)
- Adverse Events (report new/assess ongoing AEs), Study Deviations, System Modifications, Device Deficiencies

\* The echo must be sent to the Echo Core Laboratory for analysis, with a copy of the echo remaining at the site. Details of the Echo Core Laboratory, type of echo to be performed, and the review process will be provided in an Echocardiography Handbook (provided under separate cover).

\*\* The blood sample must be sent to the Blood Core Laboratory for analysis. Details of the blood core lab and the blood draw process will be provided under separate cover.

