## **10.15. Study Exit**

Subjects will be exited from the study for any of the following situations:

- Study completed
- Subject death
- Subject lost to follow-up
- Subject chooses to exit (i.e. revokes informed consent)
- Investigator withdraws subject
- Subject has intolerable symptoms that cannot be alleviated by reprogramming

A Study Exit eCRF needs to be completed for all subjects with the date and reason for the exit. The following should also be collected if applicable:

- Scheduled/Unscheduled Follow Up eCRF, if applicable
- Adverse Events, Study Deviations, System Modifications, Device Deficiencies

The finger pulse oximeter should be returned to the site at the study exit visit. After all study tests and procedures have been completed and just prior to subject exit from the study, the subject may be informed (verbally or in written form) of the subject's randomization assignment.

Following exit, subjects will continue to receive standard medical care and should be managed and followed per physician discretion. There will be no further required study-related follow-up visits for these subjects.

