#### Analysis Methods

These analyses will be exploratory in nature, involving characterizing changes from baseline and end of therapy to the last follow-up visit.

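### Protocol 7.2 promises at least 4 weeks of follow-up after pacing stops, but the Table 5 windows give the ON arm 14 to 42 days (28 at target)

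*Protocol*

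**What the plan says.** Protocol 7.2 (Rationale) states: "All subjects will be followed for at least 4 weeks following termination of the elevated night pacing therapy". It gives the reason: to see whether changes in quality of life, walk distance and echo measurements last once therapy has ended, and to follow the time course of any reversal.

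The timing rules are elsewhere:

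- **When pacing stops.** The OFF arm is reprogrammed at the 4 week visit. For everyone else, Section 10.12.1 says: "All subjects should have elevated night pacing OFF by the end of the 8 week visit".
- **When follow-up ends.** Section 10.14 makes the 12 week visit the last one.
- **Windows.** Table 5 allows days 21 to 35 for the 4 week visit, 49 to 63 for the 8 week visit and 77 to 91 for the 12 week visit, all counted from Baseline.
- **Off-window visits.** The text above Table 5 in Section 10.5 requires a deviation report, with "the original follow-up schedule maintained for subsequent visits". It adds: "Data analyses will include follow-up visits, regardless of whether the visit occurs within the window".

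The analysis that uses this follow-up is in Protocol 14.1.8, which describes "characterizing changes from baseline and end of therapy to the last follow-up visit". SAP 7.9.8 makes it specific. For ON subjects, week 12 is compared with baseline, week 4 and week 8. For OFF subjects, week 8 is compared with baseline and week 4.

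**The concern.** Section 7.2 states a floor. Table 5 delivers a target with a 15-day window at each end of the interval, and nothing ties the 12 week visit to the date pacing was switched off. A late 8 week visit does not move the 12 week visit, because the schedule stays anchored to Baseline.

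Time since therapy stopped matters for this question. The protocol's background section reports that in animal models the dilating effect of pacing fades after withdrawal. The ON arm is the larger arm under 2:1 randomization, and its only scheduled clinic visit off therapy is week 12. SAP 7.9.8 labels the comparison by visit and does not derive days since stop. A reader relying on Section 7.2 could conclude that an effect seen at week 12 had lasted at least 4 weeks off therapy. For some fully compliant ON subjects that would be untrue.

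**Working it through.** **Inputs.** Table 5: 4 week visit day 21–35 (midpoint 28), 8 week visit day 49–63 (midpoint 56), 12 week visit day 77–91 (midpoint 84). Stop of pacing: the 8 week visit for ON (Section 10.12.1) and the 4 week visit for OFF (Table 7). End of follow-up: the 12 week visit (Section 10.14). Promised minimum: 4 weeks, or 28 days (Section 7.2).

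**Formula.** Days off therapy = day of 12 week visit − day pacing is programmed OFF.

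**Reproducing the plan's figure.** At target days the ON arm has 84 − 56 = 28 days. So 4 weeks is the nominal value for that arm.

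**Range with all visits in window and pacing stopped on schedule.**

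| Arm | Minimum | Target | Maximum |
|---|---|---|---|
| ON | 77 − 63 = 14 | 84 − 56 = 28 | 91 − 49 = 42 |
| OFF | 77 − 35 = 42 | 84 − 28 = 56 | 91 − 21 = 70 |

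The ON minimum is half the stated floor, and the ON extremes differ by a factor of 42/14 = 3. The OFF minimum is above 28 days, so the statement always holds there.

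**When the ON arm falls short.** Let *a* be the 8 week visit's distance from day 56 and *b* the 12 week visit's distance from day 84, each between −7 and +7. Days off therapy = 28 + *b* − *a*. This is below 28 exactly when *b* < *a*, and equals 28 whenever both visits are shifted by the same amount (days 49 and 77, or 63 and 91, for example).

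| 8 week visit | Days off therapy | 12 week days giving ≥ 28 |
|---|---|---|
| Day 49 | 77 − 49 = 28 to 91 − 49 = 42 | 15 of 15 |
| Day 56 | 77 − 56 = 21 to 91 − 56 = 35 | 8 of 15 |
| Day 63 | 77 − 63 = 14 to 91 − 63 = 28 | 1 of 15 |

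Over all 15 × 15 = 225 in-window day pairs, 105 give fewer than 28 days, 15 give exactly 28 and 105 give more. That makes 120 pairs at 28 or above.

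**Off-window illustration.** If the 8 week visit falls on day 70, one week late, and the original schedule is kept, an in-window 12 week visit leaves 77 − 70 = 7 to 91 − 70 = 21 days. Such visits are still analysed.

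**The OFF arm's week 8 comparison.** Days from stop to this visit run from 49 − 35 = 14 to 63 − 21 = 42. This does not breach Section 7.2, since OFF subjects are followed to week 12. It is why the interval should be derived for every off-therapy visit and not only the last.

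**Outside these ranges.** Three groups are not covered: subjects whose pacing is stopped early on safety grounds, for whom Section 10.11 says "The subject should continue to be followed through the 12 week visit"; the reprogramming that Section 10.14 provides at week 12 "for subjects who still have their pacemaker programmed to elevated night pacing ON"; and early exits under Section 10.15, such as "Subject has intolerable symptoms that cannot be alleviated by reprogramming". The finding does not depend on them.

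**The case against.** The strongest reply is that the sentence is nominal. It sits in a rationale section, and *at least* can be read as covering the two arms: pacing ends at week 4 or week 8 and exit is at week 12, so nominal follow-up is 8 or 4 weeks. Table 5 is the operative rule. It is clear and internally consistent, and a site following it would not be misled. Windows of ±7 days make any such statement inexact. The sustained-effects work is exploratory, and its specific tests run only for measures already found significant at week 4 or week 8. The change from end of therapy to last visit is a valid quantity at any gap.

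Most of this stands, and it limits the weight of the point. It does not rescue the sentence, which applies a minimum to all subjects without qualification, while Section 7.1 describes 12 weeks of participation as approximate. A window around a target does not deliver a minimum unless the gap is controlled.

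Two stronger readings should be resisted. A reader might infer that the promise is met only when both visits fall on their target days. Equal shifts also give 28 days, and 120 of the 225 day pairs give 28 or more. A reader might also take 105 of 225 (46.7%) as the share of ON subjects who will fall short. It is a count of day pairs. The documents do not say how visits fall within windows, so no share of subjects can be estimated.

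**Conclusion.** The point holds as a minor correction. As written, Section 7.2 states a minimum that the schedule does not guarantee for the ON arm: 14 to 42 days against a floor of 28. It holds for the OFF arm at 42 to 70 days. The ranges assume in-window visits and pacing switched off at the scheduled visit.

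The consequence is confined to the exploratory sustained-effects analysis, where the ON arm's week 12 result can pool off-therapy intervals that differ threefold. A reader might infer that the trial's main conclusions are weakened. The documents do not support that: no powered endpoint, sample size or error rate depends on this interval, and the 4 week and 8 week endpoints do not use it. The OFF arm also has two off-therapy clinic visits, and device activity is recorded by date, so some information on the time course survives.

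**What to change.** 1. **Protocol 7.2.** Replace the minimum with: *nominally 4 weeks (ON arm; 14–42 days for in-window visits) or 8 weeks (OFF arm; 42–70 days for in-window visits) after pacing is stopped on schedule*. SAP 7.10 already lists protocol wording errors to be corrected at the next revision, so the item can be recorded there now and needs no amendment of its own.
2. **SAP 7.9.8.** Derive the actual days from therapy stop to each off-therapy visit, and report their distribution by arm and visit beside the sustained-effects results. Any adjustment for, or restriction by, days since stop should be a sensitivity analysis only.

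The cost is one sentence and one variable built from dates already collected. A rule forcing 28 days between the 8 and 12 week visits is not recommended. After an 8 week visit on day 63, for example, it would leave only day 63 + 28 = 91 of the current window. That is a heavy constraint, and a protocol change needing IRB approval, for an exploratory comparison.
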